8. METHODS

The most of the outcomes in our study are based on questionnaires combined with an easy to perform physical diagnostic test. To avoid an extensive load on participants in the study, we have consulted a target group of older adults (<http://www.netwerk100.nl/>) to evaluate our questionnaires on time consumption, user-friendliness and feasibility. In accordance with Netwerk 100, the most appropriate questionnaires have been chosen to measure the parameters used in this study.

a. Study parameters/endpoints

a.1 Main study parameter/endpoint

The primary outcomes of the effectiveness of Coach2Move on health status is based on the level of physical activity of participants as measured by the LAPAQ questionnaire, subscale moderate activity and a physical test, the TUG [23, 24].

Success of the trial will be declared if at least one of these parameters improves while the other does not deteriorate [13].

The subscale of the LAPAQ is a comprehensive questionnaire in diverse (physical) activities of daily living with moderate intensity including walking, riding a bicycle, gardening, heavy household chores and sports activities. The questionnaire is specifically designed to assess habitual physical activity among older adults. In this study we use a modified version, which is less time consuming for both the therapist and the patient. Outcome of the test is the amount of time spent being moderately physical active. A questionnaire was chosen due to difficulties activity monitors have shown measuring active minutes and/or step count in a population of older adults. Objective activity monitors perform well at moderate or higher walking speeds, but tend to lose accuracy at decreased gait speeds [25]. Since the LAPAQ has proven to be a valid, reliable and responsive instrument for classifying physical activity in older adults, this questionnaire has been chosen as a suitable outcome [23].

The TUG is a measurement for functional mobility. The TUG is a test commonly used in PT(G) care and allows international comparison. During the test, the patient is instructed to rise out of a chair, walk 4 meters, turn, walk back and sit down on the chair. This procedure is timed. The average time in seconds this takes is the score on this test. Due to limitations of place in housing of patients, the test we use is slightly modified: patients are required to walk 3 meter instead of the usual 4. Outcome is the amount of time in seconds it takes to complete this test. Gait speed has shown to be a reliable proxy indicator for the physical condition of older adults [26].

Another aspect of this study is the investigation of the potential efficiency of the Coach2Move strategy compared to usual care physiotherapy in frail elderly patients referred to physiotherapy by a physician or patients that enter the physiotherapy practice by direct access. The study perspective is societal. The informal caregiver is included in this economic evaluation. The economic evaluation is based on the general principles of a cost-utility analysis.

Primary outcome measures for the economic evaluation, considering the 12 months follow-up period are costs and direct and indirect and QALYs (EQ-5D, derived from the EuroQoL). The incremental cost-effectiveness ratio (ICER) “cost per QALY gained” will be computed and uncertainty surrounding this ICER will be determined using a non parametric bootstrap method. A cost-effectiveness acceptability curve will be derived that is able to evaluate efficiency by using different thresholds (Willingness to Pay) for a QALY gained. The impact of uncertainty surrounding deterministic parameters on the ICER will be explored using one-way sensitivity analyses on the range of extremes.

The cost analysis measures on patient level, volumes of care (consisting of the production factors: personnel, materials and capacity in a prospective way using patient/caregiver based diaries and therapist scoring sheets [CRFs]). Per arm full cost prices will be determined using

real costs of participating practices. If not available, standard cost prices according to the Dutch guidelines for costing research will be used.

Certain procedures standard cost prices are not available real cost prices will be determined using activity based costing. This approach applies to the health care production part of the economic evaluation.

During the follow-up period costs of informal caregivers will be estimated using a caregiver-based diary (adapted version of van den Berg et al., 2006) [27] and a questionnaire on 3 months recall basis in line with the follow-up pattern of the clinical trial [28]. The friction cost-method will be applied following the Dutch guidelines for costing research [29].

Also medical costs and travel time to health care providers and related costs that patients and caregivers make will be considered (also on the basis of a diary combined with 3 months recall). Utilities from the EQ-5D will be transformed in QALY's using the trapezium method.

a.II Secondary study parameters/endpoints

To measure the level of frailty and participation the Evaluative Frailty Index (EFIP) is used. The Frailty Index is a 50-item questionnaire on deficits in health (signs, symptoms and disabilities) in multiple domains (physical, psychological, social and general health status). This Frailty Index is based on the literature and refined in Delphi rounds. It was sensitive to change in both the pilot- and the trial study. The content validity is good, psychometric properties were be tested alongside the earlier study [30]. The score on this questionnaire is expressed as the ratio of deficits present to the total number of deficits considered.

The Global Perceived Satisfaction and Effect (GPE) score is used to measure patients' satisfaction about the intervention and the perceived effect on a 7-point Likert scale ranging from very unsatisfied to very much satisfied and very much deterioration to very much improvement, respectively [31].

The Patient Specific Complaints Scale (PSC) is commonly used in PT(G) and measures the functional status of a patient. The patient selects up to three most important mobility problems in daily life, which are the most important goals to improve. The degree of hinder is scored by the patient on a 10 point numeric scale [32]. A higher score indicates a higher level of difficulty experienced in the activity mentioned.

The quality of life is tested by usage of EQ-5D questionnaire [33]. This questionnaire consists of six questions comprising 5 domains: mobility, self care, daily activities, pain and emotions. The EQ-5D is recommended where a more concise assessment is required, particularly where a substantial change in health is expected [34].

At baseline comorbidities are registered using the Cumulative Illness Rating Scale-Geriatrics (CIRS-G) [35].

The CIRS-G in combination with registration of the physiotherapy intervention during each session and registration of health care utilization will be used to explore whether a PT intervention is adjusted because of the presence of comorbidity, if the presence of comorbidity influences the effect of an intervention, and if comorbidity require other interventions than PT.

a.III Other study parameters

From the physiotherapy patient files information on demographics, medical diagnosis, cultural background and living situation (alone or with partner) are extracted. Furthermore, the number of therapeutic sessions, number of adverse events and healthcare consumption are recorded.

Information on the process of implementation of Coach2Move will be collected by usage of various methods.

The reach of the intervention is tested based on the characteristics of patients included in relation to the total group patients treated in the same practice during the study period and related to the population in the region.

Furthermore, interviews in each practice with two patients will be carried out to get insight in patient experiences in pros and con's of the intervention, the experienced effectiveness and advises to improve the intervention. Over practices, we will guarantee a representative sample of participating patients and possibly context. Moreover, group interviews with PT's and PTG's within each practice will inform us about views and experiences of facilitators and barriers in delivering the Coach2Move interventions and views on which elements on the Coach2Move were effective and which were not, and if the education, peer assessment, EPD, and measurement procedures were viewed as helpful or unhelpful in supporting them to realize behavioural change strategies including needs assessment, problem analysis, shared decisions on SMARTI goals, and monitoring feedback.

Moreover, we will interview two patients in each practice after a period of 12 months after baseline to get insight in patient experiences of maintaining (or not) any lifestyle changes in physical activity made as a result of the intervention and their views of which aspects on the program were helpful and which were less.

Another aspect of the study is to evaluate the fidelity of the PT(G)'s to Coach2Move. This is done by the scoring of quality indication scores of patient files. PT(G)'s are asked to assess patients conform the Coach2Move approach. This asks for an extensive and thorough intake to require optimal clinical reasoning during the therapeutic process.

By scoring the files on integrality of data, it can give insight in the diagnostic therapeutic process before and during the implementation of Coach2Move. Scoring will be independently carried out by two researchers. Of every participating therapist, 10 files will be scored: 5 during the control period and 5 during the implementation period.

b. Randomisation, blinding and treatment allocation

Coach2Move is rolled-out sequentially to 4 groups; each comprising 4 physiotherapy practices. The time points at which the different practices receive Coach2Move are determined at random.

Randomisation will be carried out by a random number generator operated by an external independent researcher. By the end of the trial, all practices will have implemented Coach2Move (Figure 1).

Blinding takes place at patient level. Although patients receive an information letter prior to participation, the exact goal of the study is not specified to make sure the expectations are not biased by placement in control- or intervention group. It is stated that the study focuses

on gaining a better understanding in physiotherapeutic treatment among older adults and therefore monitors health before- and after the treatment.

Since the Coach2Move strategy relies heavily on a more extensive and thorough intake including the usage of several questionnaires which otherwise would not be used with regular physiotherapy, it is therefore complicated to blind both the participants as well as the researchers since this study uses outcomes otherwise not obtained.

c. Study procedures

Participating subjects are tested on four occasions: prior to the intervention, after 3, 6 and 12 months after commencement of the intervention.

Subjects are exposed to several questionnaires on the four moments of testing. One physical test is carried out on each of these four moments.

Procedure of patients in the study:

1. Registration at physiotherapy practice
2. Information on study
3. Informed consent
4. First assessment at the start of the intervention (t0) in which a number of measures will be performed. Questionnaires: LAPAQ, EQ-5D, EFIP, PSC and CIRS-G. In addition, the modified TUG is carried out. This assessment will take approximately 60 minutes and is carried out by one of the researchers during the control period or by one of the participating PT(G)'s during the intervention period.
5. Physiotherapy treatment. In either the experimental or the control group, the physiotherapist determines the number of physiotherapy consults that are needed. This is common in physiotherapy. During the intervention period, the patient and the PT(G) will choose the best fitting intervention profile together.
6. The second assessment (t1) at three months after the start of the intervention: questionnaires: LAPAQ, EQ-5D, EFIP, PSC, GPE and healthcare utilization. Again, the modified TUG is carried out. This assessment will take approximately 45 minutes.
7. The third assessment (t2) at six months after the start of the intervention. Questionnaires: LAPAQ, EQ-5D, EFIP, PSC, GPE, healthcare utilization and adherence. The modified TUG is performed. This assessment will also take approximately 45 minutes and is carried out by the researcher.
8. The fourth assessment (t3) at twelve months after the start of the intervention. Questionnaires: LAPAQ, EQ-5D, EFIP, PSC, GPE, healthcare utilization and adherence. The modified TUG is carried out once again. This assessment will also take approximately 45 minutes and is carried out by the researcher.

A randomised selection of participants is asked to join in focus group meetings to share experiences on Coach2Move. Participation is voluntarily.

All participants will be debriefed after the study by sending an information brochure concerning the most important outcomes and conclusions of the study. In addition, the participating practices for physiotherapy will be sent the same information in flyer format, which they can hang in a visible spot in their practice. Dutch magazines and newspapers will be approached to publish the research outcomes, as has happened during the previous trial of Coach2Move.

Procedure of enrolled therapists in the study:

1. Start with physiotherapeutic care as usual.
2. Electronic medical record (EPD) will be provided to support clinical reasoning and monitoring the process.
3. Intake is performed by the PT(G), alongside of an extensive intake carried out researcher of Radboudumc during the control period. During the intervention period, the PT(G) is charged with the extensive intake.
4. Web-based e-learning on Coach2Move
5. Coach2Move introduction through a two-day education program
6. Extensive physiotherapeutic intake under supervision of a researcher
7. Peer assessment meetings
8. Physiotherapeutic treatment conform Coach2Move approach
9. Physiotherapeutic intake takes place without presence of a researcher.
10. Focus groups on process evaluation of implementation

d. Withdrawal of individual subjects

Participating patients can leave the study at any time for any reason if they wish to do so without any consequences. Treatment will be continued accordingly. This means that during the control period physiotherapeutic treatment will be continued corresponding regular care, whereas during the intervention period treatment will be continued conform Coach2Move strategy, since Coach2Move will be provided to all patients. The investigator can decide to withdraw a subject from the study for urgent medical reasons. Their collected data however, will still be analysed.

Participants suffering from dementia will be treated according to the Code of conduct: incapacitated elderly. In consultation with their informal caregiver, the choice could be made to withdraw from the study.

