Intervention: The Coach2Move approach is stepwise implemented in 16 physiotherapy practices. On each site, at least one physiotherapist in geriatrics and one physiotherapist will receive a two-day training in the Coach2Move approach, which makes use of elements of the Hypothesis Oriented Approach for Clinicians (HOAC-II) and the International Classification of Functioning and Health (ICF). Participants receive physiotherapy according to the Coach2Move approach instead of the usual care physiotherapy.

Main study parameters/endpoints: In this study, each participant is measured four times. The first, being the baseline measurement (T0) is prior to physiotherapeutic treatment, while the second is directly after ending the treatment (T1). The following two are respectively six- (T2) and twelve months (T3) after the moment the participant started the treatment.

The primary outcome measures are the cost per quality-adjusted life year (QALY) gained, mobility measured by the modified Timed up and Go (TUG) and the level of moderate physical activity (LAPAQ). Secondary outcomes include: quality of life (EQ-5D), the degree of frailty (Evaluative Frailty Index for Physical activity), perceived effect (Global Perceived Effect and Patient Specific Complaints) and health care utilization costs.

In addition, qualitative data of experiences in implementation of Coach2Move will be gathered from interviews with patients and focus groups with PTG's and PTs.

The quantitative analysis will be based on quality indicators of medical records of patients for each physiotherapist scored by the researcher. The files in the control period are compared with those after implementation of Coach2Move.

Nature and extent of the burden and risks associated with participation, benefit and group relatedness: The physiotherapeutic process according to the Coach2Move strategy does not have more risk compared to usual care physiotherapy. The additional load related to the study participants are being exposed to consists of the three measurement moments in which questionnaires are being conducted. These moments each will take the patients approximately 60 minutes.

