9. STATISTICAL ANALYSIS

Descriptive statistics (mean, SD, proportions) will be used to report patient and PT(G) characteristics. Results on pre-structured questions on the interviews will be analysed using descriptive statistics (mean, SD, proportions).

The scores on the quality indicators of the patient files will be summarized using descriptive statistics. Descriptive summaries and charts will be produced presenting the quantitative results of the process analysis to help identify patterns of potential incomplete delivery.

a. Primary study parameter(s)

Cost-Effectiveness Analysis (CEA):

The Incremental cost-effectiveness ratio (ICER) “cost per Quality-Adjusted Life Year (QALY) gained” based on EQ-5D utilities will be computed and uncertainty will be determined using an appropriate method such as: the bootstrap method, Taylor expansion or the Fieller confidence interval method. A cost-effectiveness acceptability curve will be derived that is able to evaluate efficiency by using different thresholds (Willingness to Pay) for a QALY.

The cost analysis exists of two main parts. The direct costs of the regular physiotherapy and Coach2Move intervention will be determined on a per patient basis. Further, on patient level, volumes of care will be measured prospectively using medical records and cost questionnaires. Also travel time to the therapeutic sessions and related costs patients make will be considered.

The second part of the cost analysis consists of determining the cost prices for each volume of consumption in order to use these for multiplying the volumes registered for each participating patient. The Dutch manual for costing in evaluation analyses will be used [29]. For units of care/resources where no guideline or standard prices are available real cost prices will be determined. Research has shown that QALY's can be determined by applying a scoring method, such as developed by Versteegh and colleagues, on a meaningful health state classification measure, such as the EQ-5D. By means of the Dutch tariff, valuations can be determined for all possible health states as measured by the EQ-5D [27].

b. Secondary study parameter(s)

Quantitative Data Analysis

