10. ETHICAL CONSIDERATIONS

a. Regulation statement

This study will be conducted according to the principles of the Declaration of Helsinki (version 64, Fortaleza, 2013) and in accordance with the Medical Research Involving Human Subjects Act (WMO).

b. Recruitment and consent

Patients will be recruited in sixteen physiotherapy practices within a 12 month time period. All patients are consecutive patients that meet the inclusion criteria of this study, either referred to physiotherapy by a physician or contacting a physiotherapist by direct access because of mobility problems. Initial information on the study will be given by the secretary of the physiotherapy practice. The secretary will also give an information letter to the potential participants. The investigator of this study and an independent contact person can be approached for questions. The potential participant will get the time he/she needs to think about participation with a maximum of one week. However, it is recommended to commence as soon as possible considering the perceived need for treatment. The researcher will subsequently make an appointment with the participant for the first assessment and will also deal with informed consent. The data of the repeated measurements of the tests on the four assessments (0-, 3-, 6- and 12 months) will be used. Not all patients in this study are

followed for the full duration of this study. From those older adults not eligible based on the in- and exclusion criteria, only clinical data is analysed.

c. Objection by minors or incapacitated subjects

Older adults suffering from mild dementia are eligible to be included in the study as well. Guardians and/or (family) care givers are asked to sign a modified informed consent with strict arrangements when to withdraw the participant. These arrangements are conform Code of Conduct: Incapacitated Elderly.

d. Benefits and risks assessment, group relatedness

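### The 3-month recall cost questionnaire at 3, 6 and 12 months misses months 6 to 9, and the diary that might fill the gap is not specified

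*Combined protocol and SAP*

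**What the plan says.** All references are to the combined protocol and SAP.

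- **Horizon.** Section 8.a.1 sets it: "Primary outcome measures for the economic evaluation, considering the 12 months follow-up period". The perspective is societal and includes the informal caregiver. EQ-5D utilities are turned into QALYs by the trapezium method.
- **Visits.** Section 8.c places the assessments "prior to the intervention, after 3, 6 and 12 months after commencement of the intervention", and section 10.b agrees: "the four assessments (0-, 3-, 6- and 12 months) will be used". The last is described as "The fourth assessment (t3) at twelve months after the start of the intervention". No contact at month 9 is described. The Summary (section 1) times T1 differently: "while the second is directly after ending the treatment (T1".
- **Informal care costs.** Section 8.a.1: "During the follow-up period costs of informal caregivers will be estimated using a caregiver-based diary", together with "a questionnaire on 3 months recall basis in line with the follow-up pattern of the clinical trial".
- **Medical and travel costs.** The same section uses a diary together with the 3-month recall.
- **Volumes of care.** Section 8.a.1 names patient and caregiver diaries and therapist scoring sheets (CRFs). Section 9.a says "volumes of care will be measured prospectively using medical records and cost questionnaires" and names no diary. Section 8.a.III adds that the number of sessions and healthcare consumption are recorded.
- **Instruments per visit.** Section 8.c lists a healthcare utilization questionnaire at t1, t2 and t3. It gives no recall period and lists no diary.

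**The concern.** A 3-month look-back covers follow-up completely only if the visits are at most 3 months apart. The last interval, from T2 to T3, is 6 months, so its first half is never asked about.

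Cost per QALY is named among the primary outcomes in the Summary and is the primary analysis in section 9.a. The QALY side spans the full year because the trapezium method interpolates utility between months 6 and 12. Costs taken from recall alone would span nine months. Section 9.a gives no rule for costing an interval that was not observed. For such items the numerator and denominator of the ICER would cover different periods, and the acceptability curve would inherit the mismatch.

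The timing matters because the trial expects lower costs through a lasting change in activity (Summary; section 2), so costs in the second half of the year are of direct interest. Resource use that was never asked about cannot be recovered after the 12-month visits are done.

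**Working it through.** The plan gives no figure for cost coverage, so there is none to reproduce.

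**Inputs.** Horizon H = 12 months (8.a.1). Recall r = 3 months (8.a.1). Visits v = 3, 6 and 12 months (8.c, 10.b).

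**Coverage with T1 at 3 months.** Coverage is the union of the windows [v − r, v] within 0 to H, divided by H.

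- T1: [0, 3]
- T2: [3, 6]
- T3: [9, 12]

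The union is 3 + 3 + 3 = 9 months, and 9/12 = 75%. The gap is months 6-9, or 3/12 = 25%.

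**Coverage with T1 at the end of treatment.** The plan fixes no month for this reading, so T1 = t is an assumption, shown over a range.

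- For t below 3, the windows are [0, t], [3, 6] and [9, 12]. Coverage is (t + 6)/12.
- For t from 3 up to 6, the windows are [t − 3, t], [3, 6] and [9, 12]. Coverage is (12 − t)/12.

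| T1 (assumed month) | Coverage | Gaps (months) |
|---|---|---|
| 1 | 7/12 = 58% | 1-3 and 6-9 |
| 2 | 8/12 = 67% | 2-3 and 6-9 |
| 3 | 9/12 = 75% | 6-9 |
| 4 | 8/12 = 67% | 0-1 and 6-9 |
| 5 | 7/12 = 58% | 0-2 and 6-9 |

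The 6-9 gap is present in every row. Any other T1 adds a second gap early in follow-up.

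**QALY coverage.** The trapezium method sums (u₁ + u₂)/2 × Δt over adjacent assessments. With assessments at 0, 3, 6 and 12 months the intervals are 3 + 3 + 6 = 12 months, which is 100%.

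**Which cost items depend on the recall.**

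| Item | Sources named | Unobserved share, T1 at 3 months |
|---|---|---|
| Physiotherapy sessions | CRFs, physiotherapy files | can be 0% |
| Care outside the practice | diary, recall; medical records (9.a) | 0% if records or a continuous diary hold it; 25% if recall alone |
| Informal care | diary, recall | 0% with a continuous diary; 25% if recall alone |
| Travel | diary, recall | 0% with a continuous diary; 25% if recall alone |

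These are shares of time, not of cost. They become cost shares only under an assumption about accrual. With even accrual over the year, a recall-only item and its between-condition difference are understated by 25%. If the difference arises evenly over months 6-12 only, 3/6 = 50% of it falls in the gap. The documents give no figure to choose between these cases.

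**Effect of asking back to the previous assessment.** The windows become [0, T1], [T1, 6] and [6, 12]. Coverage is 12/12 = 100% wherever T1 falls.

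**The case against.** The strongest reply is that recall is not the only source. The sentence that sets the 3-month recall for informal care also names a caregiver diary, medical and travel costs have a diary as well, and section 8.a.1 describes prospective measurement with diaries and CRFs. Section 8.c lists questionnaires at visits, so a diary kept between visits need not appear there. That list also omits the informal-care questionnaire and the CRFs, so it is not a full inventory of cost sources. Section 9.a adds medical records, which carry no 3-month limit, and speaks of prospective measurement.

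Much of this stands. A reader might infer that a quarter of the cost horizon is missing from the cost-per-QALY analysis, or that each condition's total cost and the cost difference are 25% too low. The documents do not support either inference. Both need every cost to rest on recall alone, and the second also needs even accrual. Sessions are held in files and CRFs, and other items may be held in records or a diary.

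The diary still cannot be relied on to close the gap. The plan does not state what period it covers, when it is issued or returned, or how it combines with the recall. A diary kept only for each recall window would leave the same three months blank. The analysis section does not name it as a source. The Summary's burden statement counts only the measurement sessions as extra load, which does not fit a diary kept for a year.

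A second reply is that a longer recall trades a gap for recall error in people aged 70 or over, some with mild dementia. That is a real cost, but a smaller one than having no information on the interval.

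**Conclusion.** The concern holds for the recall questionnaire. As scheduled, it covers 9 of 12 months and misses months 6-9. If T1 is at the end of treatment, coverage falls to 58-67% when that is month 1, 2, 4 or 5.

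The consequence for the economic evaluation differs by item. With T1 at 3 months, the unobserved share of the period is 25% for an item measured by recall alone, most plausibly informal care, travel and care outside the physiotherapy practice. It can be 0% for an item held in records or CRFs, or in a diary kept throughout follow-up. The documents do not settle which case applies to which item, so neither the size nor the direction of any error in the ICER can be stated.

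This rests on two readings: that the 3-month recall applies at each follow-up visit, including T3, as section 8.a.1 indicates, and that no 9-month contact exists, since none is described. It is more than a missing detail, because a stated recall window at stated visits loses primary-outcome data that cannot be collected later.

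**What to change.** - Have each cost and informal-care questionnaire ask about the whole period since the previous assessment, so that T3 covers months 6-12. Use the same wording and recall period in the control and intervention conditions. This also closes the second gap that a variable T1 would open.
- Name the same cost sources, item by item, in sections 8.a.1, 8.c and 9.a, and state how they are combined when two sources cover the same item.
- Reconcile the timing of T1 between the Summary and section 8.c, because it sets the first two recall periods.
- If the sponsor prefers to rely on the diary, state that it is kept continuously through month 12, say when it is issued and collected, and name it in sections 8.c and 9.a.

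The cost is small: no extra visit, a changed reference period on an existing questionnaire, and somewhat more recall error at T3 in an older population. The diary route avoids the longer recall but adds burden that the Summary's burden statement would then have to include.
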